## 8. Study Procedures

### 8.1. Schedule of Events

Evaluation / Visit	Pre-Implant	Implant 	Discharge	1 Month	6 Months	1 Year	Annual (2-5 Years)
Visit Window	Within 24 weeks prior to Implant procedure unless otherwise specified	Implant procedure date	Prior to hospital discharge, or at 30 days post-implant if subject remains hospitalized	Between 2 and 6 weeks after implant	Between 23 and 29 weeks after implant date	Between 44 and 60 weeks after implant date	Between ±8 weeks after the implant anniversary date
Informed Consent	X						
Screening Committee Review	X						
Clinical Assessment	X		X	X	X	X	X
TPV Implant		X					
Echo	X 		X	X	X	X	X
Functional Cardiac Magnetic Resonance Imaging	X 			X 	X		To be completed at 2 & 5 Year Follow-Up
CT Cardiac Angiography	X 		X 				
Fluoroscopy		X		X	X	X	To be completed at 5 Year Follow-Up
Chest X-Ray			X				
SF-36	X 			X	X	X	X
Assessment of Adverse Event/ Device Deficiency	X	X	X	X	X	X	X

 Post-procedure care is carried out according to the standard care of the interventional cardiologist at his/her discretion.

 Clinical Assessment includes: at baseline – subject demographic, medical history, and medication assessment; at follow-up - medication assessment, review of adverse events, and device deficiencies.

 If an echo exam has been performed for routine diagnostic purposes prior to consenting, it can be used as the pre-implant echo exam, provided it was performed within 24 weeks prior to implant. The Principal Investigator must determine if the exam contains the protocol-required data and remains adequate for subject evaluation. If subject is screen failed, functional CMR imaging was used to satisfy the inclusion criteria, and pre-implant echo was not completed within window, a deviation is not required.

 If CMR imaging is contraindicated (e.g., subject has implantable cardiac rhythm device), no deviation will be required for MRI not performed.

 If a CMR functional exam has been performed for routine diagnostic purposes prior to consenting, it can be used as the pre-implant CMR functional exam, provided it was performed within 52 weeks prior to implant. The Principal Investigator must determine if the exam contains the protocol-required data and remains adequate for subject evaluation.

 Functional CMR at the 1 month visit will be required for subjects implanted with mTPV 25.

 CT post implant will be required for subjects implanted with TPV 25 who are participating in the Post Implant CT sub-study following Appendix XII.

 If a CT cardiac angiography exam has previously been performed prior to consenting, it can be used as the pre-implant CT exam, provided it was performed within 2 years prior to implant. The Principal Investigator must determine if the exam contains the protocol-required data and remains adequate for subject evaluation (e.g. subject has not undergone significant growth in the interim). Pre-implant CT angiography will follow Appendix VII.

 CT at discharge will be required for subjects implanted with the mTPV 25 who are participating in the Post Implant CT sub-study following Appendix XII.

 SF-36 is suitable for self-administration or administration by an interviewer in person or by telephone.

 The pre-implant SF-36 can be administered after a subject has been evaluated by the screening committee but prior to implant.

 Investigators are required to evaluate and document in the subject's medical records all adverse events and device deficiencies observed in study subjects from the time they are enrolled (consented) until they are exited from the study.

## 8.2. Subject Consent

Prior to enrolling in the study, patients should be fully informed of the details of study participation as required by applicable regulations, the site's IRB/EC and by Medtronic. Informed consent must be obtained from each patient or legally authorized representative prior to conducting any protocol-induced activities beyond standard of care, by using the informed consent form (ICF) approved by that site's IRB/EC and by Medtronic. The ICF must be signed and dated by the patient or legal representative. Any additional persons required by the site's IRB/EC to sign the informed consent form must also comply. In Japan, the relationship between the patient and legal representative must be documented in the ICF and IC process if a legal representative signed the ICF.

This study has the potential to include individuals that may be considered vulnerable. The Investigator should consider the definition of vulnerable per ISO 14155, which defines vulnerable patients as: "those patients that could be unduly influenced by the expectation or benefits associated with participation or of retaliatory response from senior members of a hierarchy in case of refusal to participate. For example, this could include Individuals with loss of autonomy due to immaturity or through mental disability, persons in nursing homes, children, impoverished persons, subjects in emergency situations, ethnic minority groups, homeless persons, nomads, refugees, and those incapable of giving informed consent. Other vulnerable subjects could include, for example, members of a group with a hierarchical structure such as university students, subordinate hospital and laboratory personnel, employees of the sponsor, members of the armed forces, and persons kept in detention." Any additional requirements by the site's IRB/EC or local regulations regarding the informed consent process requirements relating to vulnerable populations must be followed.

Informed assent should be considered depending on the age and understanding of the subject per IRB/EC requirement and local regulations or when the investigator feels that a minor cannot understand the content of the ICF sufficiently before a minor will be enrolled in the study. When required, informed assent must be obtained using the IRB/EC approved form.

*Medtronic Confidential*

Prior to the patient or legal representative signing the ICF, the investigator or authorized designee will fully explain to the patient or legal representative the nature of the research, study procedures, anticipated benefits, and potential risks of participation in the study. The investigator or designee will allow adequate time for the patient or legal representative to read the consent form and to ask questions. Signing the ICF serves to document the written and verbal information that the investigator or designee provided to the patient or legal representative, the patient or legal representative's understanding of the information, and their agreement to participate. The case history for each patient shall document the entire informed consent process including who participated in the consent discussions and that informed consent was obtained prior to participation in the study. The original signed consent form will be retained in the patient's study records and a copy of the informed consent will be provided to the patient or legal representative.

The point at which the ICF (and informed assent as applicable) is executed by all parties will be considered the point of enrollment for this study, and the subject will be assigned a subject ID number.

The ICF will be revised whenever important new information becomes available, or there is an amendment to the protocol which necessitates a change to the ICF. All revisions to the consent form must be approved in advance by the IRB/EC and local regulatory body, as appropriate. The subject should be re-consented according to IRB/EC requirements following the process as described above. If required, the investigator or designee should re-consent the subject in a timely manner.

### 8.3. Subject Screening

All consented subjects will be assigned a subject ID and will be considered enrolled into the study. All consented subjects who exit the study prior to study completion will have the reason for exit documented on the Study Exit case report form as well as in the medical record.

After obtaining informed consent, the following process for patient screening will be followed:

1. The study site will assign a unique subject ID number to all enrolled (consented) subjects.
2. The subject will have transthoracic echocardiography (TTE) and cardiac magnetic resonance (CMR) exams to assess pulmonary regurgitation and RV size and function, if not already performed per requirements given in [REDACTED]  
[REDACTED]  
[REDACTED]
3. Subjects that do not meet echocardiographic and/or CMR criteria will be exited from the study. Subjects that meet the echocardiographic and CMR criteria will undergo baseline cardiac

[REDACTED]  
[REDACTED]  
[REDACTED]  
[REDACTED]  
[REDACTED]

*Medtronic Confidential*

computed tomography (CT) angiography per [REDACTED]  
[REDACTED]

4. Anatomic measurements will be performed by Medtronic from the CT images and evaluated per device sizing guidelines given in [REDACTED]  
[REDACTED]
5. It is possible that subjects deemed eligible for implant may not meet all sizing guidelines due to variation in RVOT anatomy. The investigator can use the criteria described in [REDACTED]  
[REDACTED] as a guideline to assess the subject's candidacy for TPV implantation
6. Medtronic will provide the sizing evaluation (perimeter plot) to the investigator. If the Investigator considers the subject anatomically suitable for implantation of the Harmony TPV, the following clinical information from the subject will be submitted to the Screening Committee:
  - a. Clinical assessments and medical history
  - b. Echocardiographic, CMR, and CT data on anatomical suitability
7. The Screening Committee will review the screening data and provide a recommendation to the investigator, including valve size, who will make the final determination of implantation suitability. If it is determined the subject's anatomy is not suitable for implantation, the subject will be exited from the study. Subjects originally screened for TPV 22 who were exited due to screen failure may be re-screened for TPV 25 or mTPV 25 after being re-consented. For those subjects re-screened, a unique subject ID will be assigned.
8. Subjects who are determined to be device candidates by the investigator are eligible for cardiac catheterization and Harmony TPV implantation. Implant attempt is considered the point at which the investigational product is introduced into the subject's body. Implantation procedures are described in the IFU document.

## 8.4. Harmony TPV 25 Roll-In Phase

Prior to any implant of the Harmony TPV 25, there will be a Roll-In phase to include a cohort of subjects for the implant of the TPV 25.

### Roll-in Objectives:

The objective of the Harmony TPV 25 Roll-In Phase is to confirm the procedural feasibility, hemodynamic performance and safety profile of the Harmony TPV 25 prior to the Harmony TPV 25 becoming available for implant at all sites. Also, the Roll-In phase is intended provide Study Proctors familiarity and added expertise in the implant technique for Harmony TPV 25 prior to proctoring all sites in implanting the Harmony TPV 25.

### Roll-in Methodology:

Subjects enrolled in the Roll-in phase will follow all methods and procedures according to the CIP. This section will provide information on methods and requirements specific to the Roll-in phase of the study.

*Medtronic Confidential*

**Roll-in Phase Design:**

The Roll-in phase is specific to the initial implants of the Harmony TPV 25, to confirm the procedural feasibility, hemodynamic performance and safety profile of the device before all sites can implant the Harmony TPV 25. This phase of initial Harmony TPV implants will be limited to the investigative sites with experienced implanters (Study Proctors).

**Investigative Sites:**

The Roll-in subjects will be implanted at up to four investigative sites where the implanting physician is an experienced implanter and is currently proctoring other sites on the Harmony TPV implantation procedure (Study Proctor).

**Number of Subjects:**

A minimum of five and up to eight qualifying subjects will be implanted with the Harmony TPV 25 at up to four Study Proctor sites. Each Study Proctor site can implant up to three subjects.

**Subject Selection Criteria**

Prospective subjects for the Roll-in phase must meet all subject selection criteria for enrollment in the Medtronic Harmony TPV Clinical Study (see Section 7. Selection of Subjects).

**Informed Consent:**

Prior to enrolling in the study, patients will be fully informed of the details of study participation in the Roll-In Phase as required by applicable regulations, the site's IRB/EC and by Medtronic.

**Screening and Enrollment:**

See Section 7. Selection of Subjects for screening and enrollment information.

**Roll-in Cohort Analysis:**

The procedural feasibility, and hemodynamic performance and safety profile at hospital discharge following Harmony TPV 25 implantation of the Roll-In cohort will be analyzed. The outcome measures are defined as:

**Procedural Feasibility:**

- No device- or procedural-related mortality, with
- successful access, delivery and removal of the delivery system, and
- deployment and correct positioning (including minor repositioning if needed) of the device.

**Hemodynamic Performance:**

- Mean RVOT gradient  $\leq$  40mmHg as measured by echocardiography

**Safety Profile:**

None of the following device- or procedure-related serious adverse events:

*Medtronic Confidential*

- Life-threatening major bleed
- Major vascular or cardiac structural complications required unplanned reintervention or surgery
- Pulmonary embolism

Roll-in cohort subjects will be followed per the CIP. Roll-in data for the follow-up phase will be included in the 40-subject pivotal cohort as approved by FDA.

If Roll-in phase outcome measures are met and no concerns are raised by the DMC, Steering Committee or Medtronic, the Harmony TPV 25 will be made available to all participating Harmony TPV study sites. Harmony TPV 25 subjects implanted following the Roll-in phase will also be included in the 40-subject pivotal cohort.

## 8.5. Addition of mTPV 25 Cohort

Following the completion of the 40 pivotal cohort of TPV 22 and TPV 25, the TPV 25 was modified. There will be an added cohort of up to 15 subjects implanted with the mTPV 25. This additional cohort will include 10 US implants and up to 5 OUS implants from Canada and/or Japan.

### **mTPV 25 Cohort Objectives:**

The objective of the mTPV 25 addition is to confirm the procedural feasibility, hemodynamic performance, and safety profile of the mTPV 25.

### **mTPV 25 Methodology:**

Subjects enrolled in the mTPV 25 cohort will follow all methods and procedures according to the CIP. This section will provide information on methods and requirements specific to the mTPV 25 cohort addition into the study.

### **mTPV 25 Study Design:**

The addition of the mTPV 25 cohort into the study will follow the same study design of the study described in **Section 5. Selection of Subjects**.

### **Investigative Sites:**

The study sites include 9 US sites, 2 Canada sites, and 1 Japan site.

### **Number of Subjects:**

There will be 10 US implants and up to 5 OUS implants from Canada and/or Japan.

### **Subject Selection Criteria**

Prospective subjects for the mTPV 25 cohort must meet all subject selection criteria for enrollment in the Medtronic Harmony TPV Clinical Study (see **Section 7. Selection of Subjects**).

*Medtronic Confidential*

**Informed Consent:**

Prior to enrolling in the study, patients will be fully informed of the details of study participation in the mTPV 25 cohort as required by applicable regulations, the site's IRB/EC and by Medtronic.

**Screening and Enrollment:**

See Section 7. Selection of Subjects for screening and enrollment information.

**mTPV 25 Cohort Analysis:**

The procedural feasibility, hemodynamic performance, and safety profile of mTPV 25 at 1 month following mTPV 25 implantation will be analyzed. The outcome measures are defined as:

**Procedural Feasibility:**

- No device- or procedural-related mortality, with
- successful access, delivery and removal of the delivery system, and
- deployment and correct positioning (including minor repositioning if needed) of the device.

**Hemodynamic Performance:**

- Mean RVOT gradient  $\leq$  40mmHg as measured by echocardiography

**Safety Profile:**

None of the following device- or procedure-related serious adverse events:

- Life-threatening major bleed
- Major vascular or cardiac structural complications required unplanned reintervention or surgery
- Pulmonary embolism

mTPV 25 subjects will be followed per the CIP. A supplemental analysis for the mTPV 25 subjects for outcomes of procedural feasibility, hemodynamic performance and safety profile will be performed separately when mTPV 25 subjects have been followed for 1 month.

## 8.6. Implant Catheterization Procedure

Cardiac catheterization is performed according to the standard procedures of the interventional cardiologist. Detailed outline of the catheterization procedure recommendations is provided in the IFUs for Harmony TPV 22, Harmony TPV 25, and Harmony mTPV 25.

The Principal Investigator is anticipated to be the primary operator for the implant procedure must stay consistent throughout the duration of the study for all implanted patients at each site, unless prior

*Medtronic Confidential*

approval is received from Medtronic. Sub-investigators with appropriate training and experience may assist in the implant procedure at the discretion of the Principal Investigator.

### 8.6.1. Post-Procedure Care

Post-procedure care is carried out according to the standard post-procedure care of the interventional cardiologist at his or her discretion. It is recommended investigators comply with the AHA/ACC guidelines for bioprosthetic tissue valves and prescribe lifelong Aspirin therapy and prophylactic antibiotic therapy prior to dental procedures. For any imaging performed (i.e. intracardiac echocardiography, transesophageal echocardiography, or other imaging) post procedure, before leaving the catheterization lab, per standard of care at the investigational site, a copy of the imaging may be requested by Medtronic for review.

### 8.6.2. Discharge Criteria

Following completion of Discharge procedures described in **Section 8.1. Scheduled of Events**, hospital discharge will occur at the discretion of the investigator.

### 8.6.3. Device Explant

In the event of a medically indicated explant of the Harmony TPV, the explanting physician will follow standard local explant procedures. Subjects will be followed through discharge of the explant hospitalization or until study closure, whichever occurs first. Study sites should attempt to obtain copies of autopsy reports and the death certificate in the event of a subject's death. Requirements specific to explantation at reoperation or autopsy are described in **Appendix IX: EXPLANT PROTOCOL**. The explanted Harmony TPV should be returned to Medtronic as outlined in **Section 6.6. Product Return**.

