## 5. Study Design

This is a prospective, non-randomized, multi-center study. Up to 40 subjects will be implanted at a total up to 15 centers in the United States, Canada, and Japan. It is anticipated that more than 40 subjects will be enrolled (i.e. consented) to meet the target of up to 40 implants as not all subjects will be anatomically suitable for implantation. No site shall implant more than 10 subjects in the pivotal cohort to avoid bias of the study results. Subjects who discontinue participation prematurely following implant will be included in the analysis of results (as appropriate) and will not be replaced in the enrollment of total study subjects implanted. All implanted subjects will receive the Harmony TPV. Each implanted subject will be followed for five years or until the subject's Harmony TPV is explanted.

The addition of the second device size (Harmony TPV 25) is intended to expand the number of patients anatomically suitable for implantation and will include a Roll-In cohort of Harmony TPV 25 subjects. The Roll-In phase is described in **Section 8.4. Harmony TPV 25 Roll-In Phase**. The addition of the larger sized valve completed the pivotal cohort of 40.

Following the completion of the 40 pivotal cohort of the TPV 22 and TPV 25, the TPV 25 was modified and is referred to as modified TPV 25 (mTPV 25). There will be an added cohort of up to 15 subjects implanted with the mTPV 25. This additional cohort will include 10 US implants and up to 5 OUS implants from Canada and/or Japan. The mTPV 25 cohort is described in **Section 8.5. Addition of mTPV 25 Cohort**. The study methods include the following measures to minimize potential sources of bias:

- A Screening Committee comprised of a subset of study investigators will confirm subject eligibility and anatomic suitability
- An external, independent Clinical Events Committee (CEC) will review and adjudicate, at minimum, all deaths and endpoint related adverse events. Safety endpoint results will be based on CEC adjudications.
- All sites will follow a standardized protocol for acquisition of echocardiographic endpoint data.
- An Echo Core Lab will evaluate all echocardiograms.
- A CMR Core Lab will evaluate all functional CMR results.
- Study endpoints, when appropriate, will be based on CEC or Core Lab assessments.
- Study sites will follow their institutional procedures for maintenance of echocardiography and imaging equipment used for assessing the study variables.

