## 8.7. Subject Evaluations

Subjects in whom the Harmony TPV was implanted will be evaluated at hospital discharge, one month, six months, one year, and annually thereafter through five years or until the Harmony TPV is explanted. Protocol-required evaluations should be performed at the study site when possible. Evaluations to be performed are summarized in **Section 8.1. Schedule of Events**. If the subject is seen at a clinic not associated with the study site, all efforts should be made to obtain copies of medical records from that visit. Data obtained from these outside medical records can be used to support data entry for that visit.

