#### Catheterized Cohort

The catheterized cohort consists of all subjects who undergo catheterization for possible implantation of the Harmony TPV.

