## 12.2.1. Primary Safety Endpoint

The primary safety endpoint is freedom from procedure or device-related mortality.

CEC adjudicated data will be used to assess the safety endpoint.

The analysis cohort will be the catheterized cohort. The endpoint will be described by Kaplan-Meier statistics. The loglog transformed two-sided 95% confidence interval using the Peto standard error at 30 days will be presented. The primary safety objective will be met if the point estimate of the freedom from procedure or device-related mortality rate at 30 days post-procedure is equal to or greater than the performance target of 95%.

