#### 7.4 Handling of Missing, Unused, and Spurious Data and Dropouts

Every effort will be undertaken to minimize missing data. In time-to-event outcomes drop-outs will be censored at the time of discontinuation, consistent with the Kaplan-Meier approach.

Unless otherwise specified in each objective, no statistical techniques will be used to impute missing data for continuous or categorical outcomes. If a subject's data are missing for any reason, that subject will not be included in that portion of the analysis. The number of subjects included in each analysis will be reported so that the reader can assess the potential impact of missing data.

In the case of partial dates, if only the month and year are known, the event or assessment will be analyzed as if it occurred on the 15th of that month. If only the year is known, the event or assessment will be analyzed as if it occurred on June 30th of that year. These resolutions of partial dates are subject to the restrictions that pre-procedure assessments must occur between the enrollment date and the procedure date or within the window defined in the CIP. The post-procedure events and assessments must occur no earlier than the procedure date. According to the section 6.1 of the CIP, the windows for pre-procedure assessments are:

- CMR exam (functional): within 52 weeks prior to the implant date
- Clinical evaluation: within 24 weeks prior to the implant date

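### The 30-day safety endpoint covers every catheterized subject, but day-30 vital status is not required for those never implanted or those explanted and discharged before day 30

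*Protocol*

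**What the plan says.** **Who is analysed.** For primary safety, Protocol 12.2.1 states: "The analysis cohort will be the catheterized cohort". SAP 7.9.1.2 agrees. Protocol 12.1 defines the set broadly: "The catheterized cohort consists of all subjects who undergo catheterization for possible implantation of the Harmony TPV". It therefore includes subjects who leave the laboratory without a valve. All-cause, procedural and device-related death use the same cohort (Protocol 12.3, SAP 7.10).

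**Who is followed.** Protocol 5: "Each implanted subject will be followed for five years or until the subject's Harmony TPV is explanted". Protocol 8.7 lists the visits: "Subjects in whom the Harmony TPV was implanted will be evaluated at hospital discharge, one month, six months, one year", and then "annually thereafter through five years or until the Harmony TPV is explanted". After an explant, Protocol 8.6.3 applies: "Subjects will be followed through discharge of the explant hospitalization or until study closure, whichever occurs first". No visit and no exit time is given for subjects catheterized but not implanted.

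**How incomplete follow-up is analysed.** SAP 7.4 says that in time-to-event outcomes "drop-outs will be censored at the time of discontinuation, consistent with the Kaplan-Meier approach". SAP 7.9.2.3 gives the efficacy endpoint worst-case, best-case and carried-forward sensitivity analyses. The safety endpoint has none.

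**The success rule.** Safety is met if the 30-day Kaplan-Meier point estimate is at least 95%. There is no hypothesis test and no sample size calculation.

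**The concern.** The analysis set is wider than the group that the visit schedule follows to the endpoint time. The subjects in between are foreseeable. The plan keeps separate cohorts for attempted implant, implant, and implant lasting more than 24 hours, so it expects some failed attempts and some very early explants. The safety set rightly includes these subjects, and they are the ones for whom data at day 30 are least assured.

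The endpoint is a rare event judged on a point estimate in a small cohort, so a single death can matter. If a related death occurs after exit and is not learned of, the estimate carries no trace of it, and no planned analysis shows how much the conclusion depends on the missing information.

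**Working it through.** **Inputs from the documents**
- Target: 30-day Kaplan-Meier estimate of at least 95% (Protocol 12.2.1, SAP 7.9.1.2).
- 40 implanted subjects in the pivotal cohort, and 20 in the feasibility study that is pooled (SAP 6). The catheterized N is not stated; for the pivotal cohort it cannot be below the number implanted.
- No expected event count, power or sample size is given, so the plan has no figure to reproduce.

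**Assumptions, not in the documents**
- Catheterized N between 40 and 65.
- 1 to 5 subjects exit early and are censored at exit.
- All deaths counted are procedure- or device-related.

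**Step 1: deaths tolerated if day-30 status is complete.** The rule is (N − d)/N ≥ 0.95.
- N = 40: 38/40 = 95.0% is met; 37/40 = 92.5% is not.
- N = 45: 43/45 = 95.56% is met; 42/45 = 93.33% is not.
- N = 60: 57/60 = 95.0% is met; 56/60 = 93.33% is not.
- N = 65: 62/65 = 95.38% is met; 61/65 = 93.85% is not.

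**Step 2: planned estimate against complete ascertainment.** Let e subjects exit before any of the d observed deaths. The planned estimate is (N − e − d)/(N − e). If h of the exited subjects in fact died by day 30, the estimate with complete data is (N − d − h)/N.

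| N | e | d | Planned estimate | h | Complete-data estimate |
|---|---|---|---|---|---|
| 45 | 2 | 2 | 41/43 = 95.35%, met | 1 | 42/45 = 93.33%, not met |
| 45 | 2 | 1 | 42/43 = 97.67%, met | 2 | 42/45 = 93.33%, not met |
| 40 | 3 | 0 | 37/37 = 100%, met | 3 | 37/40 = 92.5%, not met |
| 65 | 1 | 3 | 61/64 = 95.31%, met | 1 | 61/65 = 93.85%, not met |

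**Step 3: how narrow the margin is at N = 40 with one exit.** Suppose two deaths are observed.
- Both after the exit: 37/39 = 94.87%, already not met.
- One before and one after: 39/40 × 37/38 = 94.93%, already not met.
- Both before: 38/40 = 95.0%, met. A hidden death would make it 37/40 = 92.5%.

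With one observed death and one hidden death the complete-data figure is 38/40 = 95.0%, still met. With three observed deaths the target is missed in any case. So at this size with one exit, a hidden death reverses the decision only if exactly two deaths were observed and both came before the censoring. With no observed deaths, three hidden deaths are needed.

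**Step 4: direction.** Censoring can also lower the estimate. In the first case of Step 3, had the exited subject survived, complete data would give 38/40 = 95.0% (met) against 94.87% as planned. At N = 60 with one exit and three later deaths, the planned figure is 56/59 = 94.92% against 57/60 = 95.0%.

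**The case against.** The protocol is not silent on late outcomes. Protocol 10.2 asks sites to report the final outcome of an adverse event still ongoing at exit, if it becomes known before study closure. A complication that leads to explant and later proves fatal would fall under this. Protocol 8.6.3 asks sites to seek autopsy reports and the death certificate when a subject dies, and the events committee adjudicates all deaths. A reader might infer that a related death on day 20, after discharge on day 8, would certainly not count; these provisions mean that this is not established. They do make an unseen death less likely. They do not close the gap, because none obliges a site to find out whether an exited subject is alive at day 30. The vital-status contact in 8.7.2 is triggered by a missed required visit, and these subjects have none due.

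Nor do the documents state a censoring date for explanted subjects. SAP 7.4 speaks of drop-outs, and a subject followed to explant discharge has completed what the protocol asks. For non-implanted subjects, adverse event recording runs until study exit, and no exit time is given. Censoring at exit is therefore a likely reading, not a stated rule.

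A reader might also infer that censored subjects are counted as event-free. Kaplan-Meier does not do that: it removes them from the risk set and assumes that their later risk matches that of subjects still followed.

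Finally, ending follow-up at explant is an explicit and consistent choice (Protocol 5, 8.7; SAP 5). Device success and freedom from TPV dysfunction are largely unaffected, since a device-related explant or reoperation is already a failure. The documents do not commit to 5-year death curves either: deaths may be summarised by Kaplan-Meier or by count and percent. Annual contact for five years after explant is thus a matter of preference and is not needed to repair the primary endpoint.

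**Conclusion.** The point stands in a limited form. The primary safety set includes subjects whose day-30 vital status the protocol does not require, and the existing provisions narrow that gap without closing it. For explanted subjects it touches the 30-day endpoint only if explant and discharge both precede day 30. Later explants affect only the later death summaries.

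The size cannot be fixed from the documents. Under the assumed N of 40 to 65, one unseen death is worth 1/65 to 1/40, about 1.5 to 2.5 percentage points. It changes the decision only when observed deaths are already at the limit.

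Two stronger readings are not supported. One is that a single uncounted death would generally overturn the result because 38/40 passes and 37/40 fails. Those are crude proportions on the implanted target, whereas the endpoint is a Kaplan-Meier estimate in a catheterized cohort of unstated size, and Step 3 shows how narrow the condition is. The other is that the estimate is necessarily biased upward. That requires a higher death rate in exited subjects, which is plausible after explant or failed implant but for which the documents give no figure.

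**What to change.** 1. **Protocol.** Require day-30 vital status, counted from the procedure, for every catheterized subject, including those never implanted and those explanted and discharged earlier, with events committee review of any death. Use the contact approach in 8.7.2, by phone or record review. For the pivotal cohort, whose implants are complete, use record review.
2. **SAP 7.9.1.** Add a worst-case sensitivity analysis that counts catheterized subjects with unknown day-30 status as events. In the first example of the table (N = 45, 2 exits, 2 observed deaths) it would show 41/45 = 91.11% beside the planned 95.35%.
3. **SAP 7.10.** State that later death summaries are censored at explant, with observation ending at discharge from the explant stay.

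**Cost.** A few extra contacts or record checks, a short amendment, and possibly IRB/EC approval or re-consent for subjects who have already exited. The change concerns data collection and analysis only and leaves clinical management untouched.
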